#### 4.3 Non-inclusion criteria

1. Previous or concurrent cancer that is distinct in primary site or histology from colorectal cancer within 5 years prior to study inclusion, except for curatively treated cervical cancer in situ, non-melanoma skin cancer and superficial bladder tumors [Ta (non invasive tumor), Tis (carcinoma in situ) and T1 (lamina propria invasion)].
2. Discovery of metastases within 6 months after the termination of adjuvant chemotherapy.
3. Previous treatment for metastatic disease.
4. Radiotherapy within 28 days prior to first dose of treatment.
5. Active cardiac disease including any of the following:
  - a. Congestive heart failure  $\geq$  New York Heart Association (NYHA) class 2 (appendix 3),
  - b. Unstable angina (angina symptoms at rest), new-onset angina (begun within the last 3 months),
  - c. Myocardial infarction less than 6 months before first dose of treatment,
  - d. Cardiac arrhythmias requiring anti-arrhythmic therapy (beta blockers or digoxin are permitted).
6. ECG with a QT/QTc interval higher than 450 ms for men and higher than 470 ms for women.

7. Uncontrolled hypertension. (Systolic blood pressure > 140 mmHg or diastolic pressure > 90 mmHg despite optimal medical management).
8. Arterial or venous thrombotic or embolic events such as cerebrovascular accident (including transient ischemic attacks), deep vein thrombosis or pulmonary embolism within 6 months before start of treatment.
9. Persistent proteinuria of National Cancer Institute Common Terminology Criteria for Adverse Events (NCI-CTCAE V5) grade 3 (i.e. urinary protein  $\geq 3.5$  g/24 hrs)
10. Peripheral neuropathy > grade1 (NCI-CTCAE v5).
11. Major surgical procedure, open biopsy, or significant traumatic injury within 28 days prior to first dose of treatment.
12. Ongoing infection > grade 2 (NCI-CTCAE v5).
13. Known history of human immunodeficiency virus (HIV) infection.
14. Chronic hepatitis B or C infection (if hepatitis status cannot be obtained from medical records, re-testing is required).
15. Seizure disorder requiring medication.
16. Symptomatic metastatic brain or meningeal tumors.
17. Evidence or history of any grade 3-4 bleeding diathesis. Any hemorrhage or bleeding event  $\geq$  Grade 3 (NCI-CTCAE v5) within 4 weeks prior to the start of study medication.
18. History of organ allograft.
19. Non-healing wound, ulcer, or bone fracture.
20. Dehydration Grade  $\geq 1$  (NCI-CTCAE v5).

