Including skin assessment for toxicities

Pre-menopausal women of childbearing potential only

12-lead ECG will be performed before and after the administration of Oxaliplatin during the three first cycles (Phase I and II) beyond cycle 3, ECG will be performed before administration of oxaliplatin

Includes: albumin, creatinine, creatinine clearance calculated according MDRD, lipase, glucose, TSH (every 6 weeks of CXD1), , total protein and uric acid

Liver function tests will be performed weekly during the three first cycles of treatment

Not required at day 1 of cycle 1 if those were completed within 7 days

Dipstick assessment with pH, protein, glucose, bilirubin, ketones, blood cells and leucocytes

CT scan of the abdomen, pelvis and chest or if the patient is allergic to iodine contrast agents, hepatic MRI and CT scan of the pelvis and chest without injection; RECIST criteria version 1.1

CT-Scans will be performed every 8 weeks

If the last radiological tumor assessment > 1 month

CT-Scan of safety follow-up will be performed if only it weren't done at the EOT visit

Period for DLT assessment is the three first cycles (only Phase I)

Height only at screening

Blood pressure will be monitored every other week during the first 3 cycles of treatment

Continuously from screening until FU visit, 30 days after last administration of study drug

A treatment diary will be handed over to patient on cycle 1 day 1

Three EDTA tubes will be collected at baseline, every 8 weeks during treatment and at the end of treatment

Paraffin-embedded human solid tissue blocks will be sent off at room temperature at the end of the enrollments

Only for unstabilized adverse events since the end of treatment

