- Drug accountability (pharmacy). To have complete control over the distribution and use of the study drug, the drug accountability must be performed on Day 1 for (Regorafenib) of each cycle.

A patient's diary is given on C1D1. It will allow to patient to write down his oral intakes and blood pressure values. It will be checked out at each cycle by C2D1.

- The blood pressure must be monitored every other week for the three first cycles of study treatment,

The blood pressure will be recorded by the patient and entered onto his treatment diary. Blood pressure measurements will be performed in patients sitting for 5 minutes prior to the evaluation.

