## 6.4 Treatment duration

12 cycles have to be delivered consecutively or not.

Indeed, treatment can be temporarily stopped to perform surgical resection or regional procedures (radiofrequency, cryoablation, radiation therapy) if the disease become accessible to them but if it happens, before the end of the 12 planned cycles, the treatment

has to be resumed within 4 to 8 weeks after the loco-regional procedure has been completed in order to reach a total number of 12 cycles delivered.

If a surgery or a regional procedure is considered, we recommend respecting a time period of 4 weeks between the last chemotherapy and the procedure.

After 12 cycles, patients whose metastases are not progressing and are still unresectable will receive regorafenib (experimental regimen and at the same dose) until progression or toxicity.

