**Table 12 : Dose modification/interruption and management of treatment-emergent hypertension**

Severity grade	Definition	Antihypertensive therapy	Dose modification/interruption
Grade 1	Prehypertension: SBP 120-139 mmHg or DBP 80-89 mmHg	None	Continue study drug. Consider increased BP monitoring
Grade 2	SBP 140-159 mmHg or DBP 90-99 mmHg or symptomatic increase in DBP >20 mmHg or to >140/90 mmHg if previously within normal limits	Treat with the aim to achieve DBP $\leq$ 90 mmHg. If S/DBP previously within normal limits, start antihypertensive monotherapy. If subject is taking antihypertensive medication, titrate the dosage up.	Continue study drug. If symptomatic, delay dose until symptoms resolve AND diastolic BP $\leq$ 90 mmHg Restart dose at same dose level.
Grade 3	SBP $\geq$ 160 mmHg or DBP $\geq$ 100 mmHg or $\geq$ 1 antihypertensive drug or more intensive antihypertensive therapy required than previously	Treat to DBP $\leq$ 90 mmHg. Start antihypertensive medication. and/or Increase dose of current antihypertensive medication. and/or add additional antihypertensive medication(s)	Delay dose until DBP $\leq$ 90 mmHg and, if symptomatic, until symptoms resolve. A restart dose will be at the same dose level. If BP not controlled with more intensive therapy, reduce dose to Dose reduction step -1 If Grade 3 hypertension recurs after dose reduction and antihypertensive therapy, reduce dose to Dose reduction step -2
Grade 4	Life-threatening consequences (malignant hypertension): transient or permanent neurologic deficit, hypertensive crisis	--	Discontinue therapy

In cases only one value is >Grade 1 (e.g., 155/88 mmHg), the guidelines provided for the highest grade should be followed. Patients requiring interruption of study treatment > 4 consecutive weeks must discontinue study drug.

If BP remains controlled for  $\geq$  one full cycle, dose re-escalation is permitted at the investigator's discretion

Blood pressure will be recorded by the treating physician and entered onto the e-CRF.

Any blood pressure that is out of normal range must be reported to the treating physician.

Blood pressure measurements considered out of normal range are diastolic  $\geq 100$  mmHg and systolic  $\geq 150$  mmHg, or a  $\geq 20$  mmHg increase in diastolic measurement if the measurement was previously within normal limits.

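### The blood pressure reporting note joins its limits with 'and' while Table 12 acts on either value, so read literally some numeric grade 3 readings need not be reported between visits

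*Combined protocol and SAP*

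**What the plan says.** Section 6.6, Table 12, sets the management of hypertension on regorafenib. By numbers, grade 2 is systolic pressure (SBP) 140-159 mmHg or diastolic pressure (DBP) 90-99 mmHg; grade 3 is SBP at or above 160 mmHg or DBP at or above 100 mmHg. At grade 3 the dose is delayed until DBP is 90 mmHg or lower "and, if symptomatic, until symptoms resolve. A restart dose will be at the same dose level".

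Three notes below the table matter here:

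- If only one of the two values is above grade 1, it still decides the management: "155/88 mmHg), the guidelines provided for the highest grade should be followed".
- There is a reporting duty: "Any blood pressure that is out of normal range must be reported to the treating physician".
- The range for that duty is then defined: "Blood pressure measurements considered out of normal range are diastolic" at or above 100 mmHg and systolic at or above 150 mmHg, or a diastolic rise of 20 mmHg or more from a value within normal limits.

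Elsewhere, section 4.3 (criterion 7) excludes patients on either value: "Systolic blood pressure > 140 mmHg or diastolic pressure > 90 mmHg despite optimal medical management". Section 5.3 gives the patient a diary on day 1 of cycle 1: "It will allow to patient to write down his oral intakes and blood pressure values". The diary is checked at each cycle from day 1 of cycle 2, and the table in section 5.1 marks that check at cycle 2, cycle 3, cycle 4 onward and end of treatment.

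**The concern.** The grading table, the single-value note and the exclusion criterion all act on either pressure. Only the reporting rule asks for both, unless diastolic pressure has risen by 20 mmHg from normal. Followed as written, it lets through readings for which the same section requires regorafenib to be held, and also the protocol's own 155/88 example.

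A physician who measures a pressure at a visit applies Table 12 directly and does not need the reporting rule. The rule therefore matters for readings taken between visits, and what is at stake is how soon the physician learns of a grade 3 value. That these are chiefly the patient's diary readings is an inference: the note does not say who must report.

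**Working it through.** The plan gives no figure to reproduce. The check applies the two rules to the same readings.

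**Inputs** (all from section 6.6, Table 12 and its notes)

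- Numeric grade 3: SBP ≥160 or DBP ≥100. Numeric grade 2, if not grade 3: SBP 140-159 or DBP 90-99.
- Literal rule: DBP ≥100 and SBP ≥150.
- Rule with 'or': DBP ≥100 or SBP ≥150.
- Rise limb, under either rule: current DBP minus earlier normal DBP ≥20, so the earlier DBP must be at or below current DBP minus 20.

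**Individual readings**

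| Reading | Grade (deciding value) | Reportable with 'and' | Reportable with 'or' | Rise limb applies if earlier DBP is at most |
|---|---|---|---|---|
| 165/95 | 3 (SBP) | no | yes | 95 − 20 = 75 |
| 170/85 | 3 (SBP) | no | yes | 85 − 20 = 65 |
| 145/102 | 3 (DBP) | no | yes | 102 − 20 = 82 |
| 155/88 | 2 (SBP) | no | yes | 88 − 20 = 68 |
| 165/102 | 3 (both) | yes | yes | not needed |
| 145/95 | 2 (both) | no | no | 95 − 20 = 75 |

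**All integer pairs** with SBP 100-220, DBP 50-130 and SBP above DBP, leaving the rise limb aside

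- Grade 3 pairs: 6,305. The literal rule misses 4,104; the rule with 'or' misses 0.
- Each missed grade 3 pair has either SBP ≥160 with DBP <100, or DBP ≥100 with SBP <150.
- Grade 2 pairs: 1,400. The literal rule misses all of them, necessarily, since DBP ≥100 is already grade 3. The rule with 'or' misses 900, all with SBP <150 and DBP <100.

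These counts test the logic. They say nothing about how often such readings occur.

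**Effect of the rise limb.** The note does not define normal DBP. If normal means below 90, 145/102 escapes when the earlier DBP was 83-89, or was already abnormal at 90 or more. If normal means below 80, because Table 12 labels 80-89 prehypertension, any DBP ≥100 is a rise of more than 20 from normal. It is then reportable unless the earlier value was itself 80 or more. On either definition the diastolic-only gap is narrow. The systolic gap is wider: 165/95 escapes whenever the earlier DBP was above 75.

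**When an unreported reading is seen.** Cycles are 14 days and the diary is checked each cycle. A diary reading is therefore seen within about 14 days while cycles run on time. The protocol does not say when home readings are taken, so the actual delay cannot be computed.

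**The case against.** The best defence is that 'and' simply lists two separate limits: the subject is plural, and the table and the 155/88 note just above treat one raised value as enough. On that reading no numeric grade 3 value is missed. The reading is possible. However, the sentence has the form 'A and B, or C', with a comma before the rise limb, and the protocol writes 'or' in Table 12 and in section 4.3 where it means either value. The joint reading is the more natural one, and both readings lead to the same edit.

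The second defence is that little depends on the rule, because the diary is checked every cycle and Table 12 then decides dosing. This stands, and it limits the point to later notice.

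A reader might also infer more than the documents support:

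- *That dose-limiting toxicities could be lost.* Toxicity is assessed at day 1 of cycles 2 to 4 and the diary is checked at the same visits. The reporting rule does not change grading, so a lost event is not shown. Nor is any effect on efficacy.
- *That the rule matters more after cycle 3.* Footnote 16 in section 5.1 reads "Blood pressure will be monitored every other week during the first 3 cycles of treatment", while section 6.4 says "12 cycles have to be delivered consecutively or not" and then continues regorafenib as maintenance. The missing later schedule is a separate matter that this edit does not touch, and the diary check is still marked from cycle 4 onward.
- *That 150 mmHg is wrong because grade 2 starts at 140.* An alert limit above the treatment limit may be deliberate.

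**Conclusion.** The inconsistency is real and confined to safety wording. Read literally, and without a diastolic rise of 20 mmHg from normal, the note leaves two kinds of numeric grade 3 reading unreported. The main kind is a high systolic value with diastolic below 100; the narrower kind is a diastolic value of 100 or more with systolic below 150.

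The consequence is that the physician may learn later of a reading that calls for a dose delay. This rests on two assumptions: that 'and' is meant jointly, and that the duty concerns readings taken between visits. The sample size and the primary analysis are unaffected. The point is minor but worth correcting, because a mandatory safety rule should not fall short of the dosing table it serves.

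**What to change.** In the note below Table 12, replace 'and' with 'or' between the two limits. The rule would then cover diastolic pressure at or above 100 mmHg, or systolic pressure at or above 150 mmHg, or a diastolic rise of 20 mmHg or more from a normal value. Make the same change in any patient instruction that repeats the rule.

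Every numeric grade 3 reading, and the 155/88 example, then becomes reportable. Grade 2 readings below both limits, such as 145/95 with an earlier diastolic above 75, stay unreported; whether to lower the alert limit for them is a separate decision for the clinical team. The cost is one word and some extra reports to the physician.

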#### Termination of regorafenib :

In the event of gastrointestinal perforation or fistula develops

In the event of reversible Posterior Encephalopathy Syndrome (REPS)

-In the event of the appearance of cardiac ischemia and/or infarction, severe bleeding, severe hypertensive crisis

### **6.7 Authorized associate procedures and treatment**

All medication which is considered necessary for the patient's welfare, and which is not expected to interfere with the evaluation of the study drug, may be given at the discretion of the Principal Investigator. All concomitant medications (including start/stop dates, dose frequency, route of administration and indication) must be recorded in the patient's source documentation, as well as in the appropriate pages of the e-CRF.

#### **6.7.1 Other treatments/procedures**

##### **Authorized concomitant medications:**

- Atropine
- Anti-emetics
- Alpha hydroxyl acids, keratolytic, non urea creams
- Topical corticoids

- Antihistaminics
- Contrast agent
- Treatment with non-conventional therapies (for example homeopathy, vitamins or acupuncture), and vitamin/mineral supplements is acceptable provided that they do not interfere with the study endpoints, in the opinion of the Investigator.
- It is advised not to use the association of warfarine (Coumadine®) with chemotherapy. It is preferable to use heparin and therapeutic anticoagulation with low-molecular weight heparin. If warfarine cannot be avoided, the rate of prothrombin must be checked more frequently and INR monitored every fortnight until INR/PTT is stable.
- Bisphosphonates
- G-CSF and other hematopoietic growth factors may be used during the study in the management of acute toxicity such as febrile neutropenia when clinically indicated or at the discretion of the investigator.
- Patients taking chronic erythropoietin are authorized.

## 6.8 Prohibited treatment

-Other antitumor treatments (chemotherapy, hormonotherapy, immunotherapy, biological response modifier, targeted therapy) or approved therapies during this trial or within 30 days are prohibited.

-St-John's wort

-Herbal medicine and grapefruit juice

-Yellow fever vaccine.

-live attenuated vaccines

-Pimozide (Orap®) and cisapride (Prepulsid®) are strictly contraindicated: they are associated with a major risk of disorder of the ventricular rhythm (notably twisting spuses).

- Immunosuppressive agents (eg ciclosporin, tacrolimus): Excessive immunosuppression with risk of lymphoproliferation.
- Bone marrow transplant or stem cell rescue.
- Radiotherapy within 28 days prior to first dose of treatment.

## 6.9 Main medications that can interact with regorafenib

### Inhibitors of CYP3A4 and UGT1A1/UGT1A9/inducers of CYP3A4

*In vitro* data indicate that regorafenib is metabolized by cytochrome CYP3A4 and uridine diphosphate glucuronosyl transferase UGT1A9.

Administration of ketoconazole (400 mg for 18 days), a strong CYP3A4 inhibitor, with a single dose of regorafenib (160 mg on day 5) resulted in an increase in mean exposure (AUC) of regorafenib of approximately 33%, and a decrease in mean exposure of the active metabolites, M-2 (N-oxide) and M-5 (N-oxide and N-desmethyl), of approximately 90%. It is recommended to avoid concomitant use of strong inhibitors of CYP3A4 activity (e.g. clarithromycin, grapefruit juice, itraconazole, ketoconazole, posaconazole, telithromycin and voriconazole) as their influence on the steady-state exposure of regorafenib and its metabolites has not been studied.

Co-administration of a strong UGT1A9 inhibitor (e.g. mefenamic acid, diflunisal, and niflumic acid) during regorafenib treatment should be avoided, as their influence on the steady-state exposure of regorafenib and its metabolites has not been studied.

Administration of rifampicin (600 mg for 9 days), a strong CYP3A4 inducer, with a single dose of regorafenib (160 mg on day 7) resulted in a reduction in AUC of regorafenib of approximately 50%, a 3- to 4-fold increase in mean exposure of the active metabolite M-5, and no change in exposure of active metabolite M-2. Other strong CYP3A4 inducers (e.g. phenytoin, carbamazepine, phenobarbital and St. John's wort) may also increase metabolism of regorafenib. Strong inducers of CYP3A4 should be avoided, or selection of an alternate concomitant medicinal product, with no or minimal potential to induce CYP3A4 should be considered.

### UGT1A1 and UGT1A9 substrates

*In vitro* data indicate that regorafenib as well as its active metabolite M-2 inhibit glucuronidation mediated by UGT1A9 whereas M-5 only inhibits UGT1A1 at concentrations

which are achieved *in vivo* at steady state. This indicates that co-administration of regorafenib may increase systemic exposure to UGT1A1 and UGT1A9 substrates.

#### Breast cancer resistance protein (BCRP) and P-glycoprotein substrates

Administration of regorafenib (160 mg for 14 days) prior to administration of a single dose of rosuvastatin (5 mg), a BCRP substrate, resulted in a 3.8-fold increase in mean exposure (AUC) of rosuvastatin and a 4.6-fold increase in  $C_{max}$ .

This indicates that co-administration of regorafenib may increase the plasma concentrations of other concomitant BCRP substrates (e.g. methotrexate, fluvastatin, atorvastatin).

#### Inhibitors of P-glycoprotein and BCRP/Inducers of P-glycoprotein and BCRP

*In vitro* studies indicate that the active metabolites M-2 and M-5 are substrates for P-glycoprotein and BCRP. Inhibitors and inducers of BCRP and P-glycoprotein may interfere with the exposure of M-2 and M-5. The clinical significance of these findings is unknown.

#### CYP isoform-selective substrates

*In vitro* data indicate that regorafenib is a competitive inhibitor of the cytochromes CYP2C8 (Ki value of 0.6 micromolar), CYP2C9 (Ki value of 4.7 micromolar), CYP2B6 (Ki value of 5.2 micromolar) at concentrations which are achieved *in vivo* at steady state (peak plasma concentration of 8.1 micromolar). The *in vitro* inhibitory potency towards CYP3A4 (Ki value of 11.1 micromolar) and CYP2C19 (Ki value of 16.4 micromolar) was less pronounced.

A clinical probe substrate study was performed to evaluate the effect of 14 days of dosing with 160 mg regorafenib on the pharmacokinetics of probe substrates of CYP2C8 (rosiglitazone) CYP2C9 (S-warfarin), CYP 2C19 (omeprazole) and CYP3A4 (midazolam).

Pharmacokinetic data indicate that regorafenib may be given concomitantly with substrates of CYP2C8, CYP2C9, CYP3A4, and CYP2C19 without a clinically meaningful drug interaction.

#### Antibiotics

The concentration-time profile indicates that regorafenib and its metabolites may undergo enterohepatic circulation (see section 5.2). Co-administration with neomycin, a poorly absorbed antimicrobial agent used for eradicating the gastrointestinal microflora (which may interfere with the enterohepatic circulation of regorafenib) had no effect on the regorafenib exposure, but there was an approximately 80% decrease in the exposure of the active metabolites M-2 and M-5 which showed *in vitro* and *in vivo* comparable pharmacological activity as regorafenib. The clinical significance of this neomycin interaction is unknown, but

may result in a decreased efficacy of regorafenib. Pharmacokinetic interactions of other antibiotics have not been studied.

#### Bile salt-sequestering agents

Regorafenib, M-2 and M-5 are likely to undergo enterohepatic circulation. Bile salt-sequestering agents such as cholestyramine and cholestagel may interact with regorafenib by forming insoluble complexes which may impact absorption (or reabsorption), thus resulting in potentially decreased exposure. The clinical significance of these potential interactions is unknown, but may result in a decreased efficacy of regorafenib.

### **6.10 Main medications that can interact with irinotecan**

-Concomitant treatments based on St-John's wort (alternative medicine) are absolutely contraindicated with irinotecan (Campto® or generic drug); this plant decreases the serum concentration of SN-38, the active metabolite of irinotecan.

-The interaction between irinotecan and neuromuscular blocking agents cannot be established. Because of the anticholinesterase activity of IRINOTECAN, drugs with anticholinesterase activity may prolong the neuromuscular blocking effects of suxamethonium and neuromuscular blockade of non-depolarizing agents may be antagonized.

-Several studies have shown that concomitant administration of cytochrome CYP450 3A4-inducing anti-convulsants (such as carbamazepine, phenobarbital or phenytoin) decreased exposure to irinotecan, SN-38 and SN38 glucuronide and reduced their pharmacodynamic effects. The effects of these anti-convulsants result in a 50% or greater decrease in areas under the curve (AUC) of SN-38 and SN-38 glucuronide. In addition to induction of cytochrome CYP450 3A4 enzymes, increased glucuronidation and biliary excretion may play a role in reducing exposure to irinotecan and its metabolites.

-One study showed that co-administration of irinotecan with ketoconazole compared to irinotecan alone resulted in an 87% decrease in AUC of APC and a 109% increase in AUC of SN-38.

-Special attention is required in patients receiving drugs known to simultaneously inhibit (such as ketoconazole) or induce (such as rifampin, carbamazepine, phenobarbital, or

phenytoin) cytochrome CYP450 3A4 metabolism. Concomitant administration of irinotecan with an inducer or inhibitor of this metabolic pathway may alter irinotecan metabolism and should be avoided.

